4.5 Eligibility Criteria

We will include all adult patients (16 years or older) with an open flexor tendon injury, who meet the eligibility criteria below.

Any questions raised about eligibility will be addressed prior to entering the participant into the study. There will be no exceptions (waivers) to eligibility criteria prior to participant inclusion into the study.

4.5.1 Participant Inclusion Criteria (at screening)

• Patients aged ≥ 16 years old

Inclusion Criteria for randomisation (confirmed in surgery)

- Complete division of FDP and FDS in zone 2 of a single finger
- Injury amenable to primary repair

4.5.2 Participant Exclusion Criteria (at screening)

- Injuries affecting more than one digit or the thumb
- Injuries outside of Zone 2
- Injuries affecting multiple zones
- Clinically infected wounds
- Closed flexor tendon injury
- Previous tendon, bone or joint injury in the affected digit
- Patient does not have capacity to give informed consent
- Patient unable to complete follow up requirements
- Contraindication to surgery

Exclusion criteria for randomisation (confirmed at surgery)

- Injuries with loss of tendon substance or skin necessitating reconstruction
- Division of both digital arteries resulting in revascularisation of injured digit
- Division of both digital nerves

Injuries are restricted to zone 2 as it is the most common injury and most challenging to manage owing to both tendons running in the flexor sheath.

Unilateral digital nerve injuries will be accepted on a pragmatic basis as they are often injured in addition to the flexor tendon. A recent study suggests digital nerve injury does not affect the outcome of zone 2 flexor tendon injuries [23].

Thumb injuries are excluded owing to the anatomy. There is a single thumb flexor tendon, and flexor sheath anatomy differs to the fingers. The rehabilitation regimen also differs.

4.5.3 Co-Enrolment

Co-enrolment is not permitted between patients who are taking part in the FLARE Trial and the FIRST Trial.

We will not exclude participants who are enrolled in any other study that allows co-enrolment provided that there is no direct conflict between the two studies or likely influence on the outcome of the FLARE study.

4.6 Interventions

Eligible and consenting patients will be randomly allocated to receive tendon repair using FDP repair alone or FDP and FDS repair.

Participants will undergo treatment as per the randomisation allocation schedule under the care of one of the participating surgeons.

4.6.1 Surgical Intervention

Study treatments should be given as soon as practical following recruitment. The timing of treatment is determined by local service pressures, however standard care is to surgically explore the wound and repair the tendons within 72 hours of presentation.

Surgical exploration and washout will be undertaken for all consenting patients. Patients that are confirmed as eligible during surgery will be allocated to receive either FDP repair alone or repair of both FDP and FDS.

A minimum 4 strand core suture will not be mandated but the number of strands will be recorded. A 4-strand core repair is standard practice for 80% of surgeons in the UK. An epitendinous suture (a suture around the outside edge of the tendon) will not be mandatory but if done will be recorded. Suture choice and technique will be pragmatic. Intraoperatively, surgeons will ensure excursion of the repaired tendon(s) through a full range of movement. Tendon sheath and pulleys will be released as needed to allow unimpeded gliding. Concomitant single digital nerve injuries will be repaired.

Choice of anaesthetic will be pragmatic and based on patient and surgeon preferences and availability.

Post-operative care will be in line with routine practice at the participating site. Usually, the wounds will be dressed and a plaster of Paris dorsal blocking splint applied.

4.7 Rehabilitation and Hand Therapy

The post-operative rehabilitation will be pragmatic and follow routine practice at individual participating sites across both treatment groups.

Participants are usually seen within seven days of their surgery by a hand therapist. All rehabilitation input will be left to the discretion of the clinical care team.

During the first four to six weeks, a splint is used to provide protected finger range of movement to reduce the risk of tendon repair rupture. The participant will follow a regimen using a dorsal blocking splint or a relative motion flexion splint with wrist splint. The choice of splint will be in discussion with the patient and therapist.

To supplement standard rehabilitation advice, all trial participants will receive standardised, hand therapy information detailing the types of exercises they may perform for rehabilitation following their injury.

A record of rehabilitation input (type of input and number of additional appointments) together with any other required investigations/interventions will be self-reported by trial participants as part of the follow up questionnaires and supplemented by data recorded at clinic visits by therapists or research staff.

Version 1.1

Participants will be asked to complete a questionnaire to document their splint adherence.

4.8 Assessments and Follow-Up

Trial participants are expected to be enrolled in the study for up to six months for follow-up. Qualitative interviews may take place after the six-month time point so as not to interfere with patient reported measure at that point.

The study assessment schedule is provided at the beginning of the protocol (see Table 5). All participants will be followed up within seven days of their surgery and then again at six weeks, three months and six months post-surgery.

All visits up to and including the three-month visit will take place where possible as a face to face visit as most centres have a routine three-month patient follow-up in clinic.

In the event of local restrictions arising from COVID-19, or where remote visits are conducted as part of routine care, trial visits may be conducted remotely via telephone or video call.

Trial participants should also attend any routine clinical appointments that may be scheduled outside of trial visits, in line with the routine care pathway at the participating site.

4.9 Outcomes

4.9.1 Primary Outcome

The primary outcome will be the Patient Evaluation Measure (PEM) score at six months postsurgery.

PEM is widely used in NIHR funded hand trauma studies and is the main PROM used for flexor tendon injuries in the BSSH UK National Hand Registry. The questionnaire assesses the process of treatment, current state of the hand, and a general assessment. The PEM asks questions relating to symptoms, satisfaction and general disability, which generates a percentage, ranging from 0%-100%, to determine a disability score [24].

PEM will also be collected at baseline, six weeks and three months post-surgery in line with the study assessment schedule (see Table 5)

4.9.2 Secondary Outcomes

Secondary outcomes will be collected at baseline, six weeks, three months and six months postsurgery in line with the study assessment schedule (see Table 5).

These timepoints will enable identification of early complications and later re-operations and gather data to inform resource use and work impact.

- PRWHE: is a 15-item questionnaire used to assess hand pain and disability in day-to-day • activities. The questions themselves evaluate level of pain and functionality; 5 questions revolve around pain levels and 10 focus on activities. A score of 100 indicates worst functional score whereas 0 represents no disability [25].
- EuroQol 5 Dimensions (5L) Score (EQ-5D-5L): measures health-related quality of life in terms ٠ of 5 dimensions: mobility, ability to self-care, ability to undertake usual activities, pain and discomfort, anxiety and depression. The EQ-5D-5L will be scored according to the User Guide [26]. EQ-5D-5L data will be collected at baseline to assess patient health related quality of life on the day (after the injury).

Version 1.1

- Complications: Information on all complications will be collected. Expected complications that will be recorded will include (but not be limited to) deep wound infection, (using Centres for Disease Control (CDC) and Prevention definition [27] superficial infection using CDC definition), rehospitalisation, nerve and skin problems.
- Total range of motion: Degree of movement at a joint. Measured with a goniometer.
- Grip strength: Grip Strength will be measured with a JAMAR Dynamometer. Both hands will be assessed. Three recordings will be performed on each side and the maximum of these three readings will be used. The measurement will be done with the subject seated, arm by the side, elbow bent at 90 degrees and the wrist in neutral position for rotation [28]. The second setting will usually be used for all subjects but patients with large hands may occasionally need to use the third setting. This reflects common practice and evidence-based practice in assessing grip strength [29]. Strength will be expressed as a % of opposite side to account for normal variation in strength during the day.
- Adherence to splint regimen. Patient self-report.
- Work outcomes. Patient self-report.
- Treatment and outcome satisfaction. Net promotor score
- Healthcare resource use: An accurate record of procedures at hospital level will be put in
 place in order to record the cost of each type of surgery and related complications via a
 surgical form specifically designed for this trial. Patient-reported questionnaires and hospital
 forms will be designed to collect information on hospital stay- (initial and subsequent
 inpatient episodes, outpatient hospital visits and A&E admissions); primary care
 consultations (e.g. GP, nurse and physiotherapy); work impact of both interventions; and
 return to work and return to normal activities.
- Adherence to therapy regimen

4.10 Qualitative Study

4.10.1 Recruitment Optimisation

Existing recruitment optimisation interventions are costly and resource intensive [30, 31] or take place after key design decisions have been made [32]. We therefore plan to undertake low-cost, rapid, recruitment optimisation work, making use of routinely collected trial information and rapid qualitative work to identify potential recruitment problems in our trial.

This mixed-methods recruitment optimisation work will be undertaken during the FLARE trial's setup and internal pilot phase so that any findings can be used to improve our approach to recruitment during the main FLARE study. Data collection will include:

1. N=10 (approximately) brief qualitative interviews with key stakeholders (including chief investigators (CIs) from FLARE and other key NIHR funded hand trials; FLARE clinical co-applicants and CTU staff). These interviews will use participants' experiences of setting up the FLARE trial to identify key obstacles to recruitment. We will also conduct interviews with CIs from other high profile hand surgery trials that were closed early due to recruitment difficulties to explore any common challenges facing hand surgery trials and lessons learned.

2. Record and review Trial Management Group Meetings to keep abreast of any challenges that are occurring during the trial's set-up period.

3. Record and review study checklists and other key trial documents (e.g. Expression of Interest forms sent to all eligible sites, Site Initiation Visit meeting minutes and correspondence; notification of study closure documents for recently closed trials) where appropriate.

Information obtained through interviews and key trial documents will be used to identify the key issues that FLARE may face with regard to recruitment, based on information from the set-up phase and internal pilot period and experience from other recent NIHR-funded hand surgery trials. This information will be combined and used to troubleshoot and develop strategies for overcoming any potential recruitment issues ahead of the main FLARE Trial.

Analysis of this information will be rapid and undertaken concurrently with data collection to allow initial troubleshooting. To facilitate this a standing agenda item on all TMG meetings, along with weekly project meetings will be held to facilitate the development of strategies for overcoming any issues identified. Where patient related factors are raised, PPI members will be engaged to strategize solutions.

At month 8, prior to the start of the main study, all information collected during the initial recruitment optimisation exercise will be integrated into the trial procedures. These research informed trial processes will be monitored over the coming months as the study progresses and will be under ongoing review and adapted further as appropriate. Feedback will be given directly to sites in this phase of the work via meetings with the trial manager/chief investigators where issues emerge.

4.10.2 Treatment Acceptability

The FLARE trial will also include a nested qualitative study. We propose to interview (n= 40) trial participants, following the primary outcome measurement at six months post-surgery. The purpose of these interviews is to ascertain vital information relating to acceptability and experience of the surgical procedure and the rehabilitation regimens.

Whilst our Patient and Public Involvement PPI work ascertained that patients would be prepared to be randomised to either single or double flexor tendon repair, there were some concerns raised relating to the potential safety of not repairing both tendons. This aspect will be explored in the qualitative work. In addition, patient views on the anaesthetic procedure used given the rapid adoption of the 'wide awake local anaesthetic no tourniquet' (WALANT) during the COVID pandemic. Our initial PPI work indicated that patients felt anaesthetic type was not important for their overall outcome but was important for patient experience and choice. We will therefore use anaesthetic type as a sampling criterion in the qualitative sampling frame and explore patient preferences and experience of anaesthetic in the interviews.

Provision of a splint and rehabilitation post-surgery is a vital part of flexor tendon repair. As three different splints are available as part of usual care following surgery, the qualitative interviews will capture the factors important to patients regarding the choice of splint and how any preferences impact on decision-making relating to the selected rehabilitation regime. As outlined in the brief, compliance to splint wearing and rehabilitation regimes is known to be problematic among this group of patients. It is important that this aspect is factored into our study design, in addition to quantitative measures of adherence we will explore this in the qualitative interviews with patients. In particular, to highlight barriers and facilitators to splint/rehabilitation compliance that can be used to inform clinical practice alongside the trial findings.

Version 1.1

In addition will we conduct semi-structured interviews with hand surgeons (n=10) and hand therapist (n=10), data collection will focus on their experience of delivering the intervention, challenges/facilitators associated with delivery of trial interventions and what information/training would be required in order to implement the findings from the trial across the NHS.

Semi-structured interviews will be conducted using either telephone, videoconference (e.g. Microsoft Teams or Zoom) or face-to-face, according to respondent preferences and practicalities. A topic guide will be developed in consultation with our PPI representatives. With permission, interviews will be recorded and transcribed verbatim. Anonymised transcripts will be transferred into analysis software to support management and retrieval of data. Data analysis will follow the principles of thematic analysis, providing an interpretive exploration of the experiences, attitudes and beliefs of different stakeholder groups [33]. Emerging codes and themes will be discussed as a team.

4.11 Participant Recruitment

The research team will work closely with the clinicians and research staff at each recruiting site to optimise the screening and recruitment procedures for their local circumstances.

All members of staff involved in eligibility sign-off and the informed consent process (including surgeons) will have training in Good Clinical Practice (GCP) or study specific training.

The NIHR Associate Principal Investigator (API) scheme will be utilised at participating sites to involve aspiring researchers to co-ordinate study recruitment. The APIs will be trained in study processes and will be supervised by the PI at the site. Participating sites will be encouraged to involve APIs, particularly "out of hours" (evenings and weekends) when research staff may not be available.

Potential participants will be provided with information about the study including a patient information sheet (PIS) at the earliest possible opportunity following presentation.

4.11.1 Recruitment Strategy

The recruitment projection for the main trial is based upon recruiting one patient per month per site based on the BSSH Flexor Tendon Audit (with an assumed consent rate of 50% of eligible patients). With staggered centre set-up and fewer recruits in the first months of site set-up, 80 patients will be recruited by month eight. The remaining 230 patients will be recruited over a further 14 months.

4.11.2 Study within a trial (SWAT)

The FLARE trial will act as a host trial for an embedded Study Within A Trial (SWAT), which aims to look at an intervention to improve recruitment.

Many interventions to improve recruitment at sites, such as site champions and incentivising clinicians with non-financial benefits are routinely used but do not have any evidence of their effectiveness. One way to provide a rigorous evaluation and evidence is to conduct a Study Within a Trial (SWAT) [34].

The objective of the SWAT is to evaluate the effect on recruitment rates using two interventions: Enhanced Associate Principal Investigator Package, and Digital Nudging.

Trainee APIs will be randomised to one of four interventions. 1) Enhanced API intervention, 2) Digital nudge email from trial coordinator, 3) both enhanced API intervention and digital nudge, 4) usual practice without enhanced API or digital nudge.

FLARE Protocol Page 26

Version 1.1

The primary outcome will be the number of recruits at a site during the six months the API is in post. A secondary outcome will be the total number of recruits over the six months following the API being in place.

Analysis will be conducted on an intention to treat basis. A Poisson regression model, containing the two interventions (enhanced API and digital nudge) and the minimisation factors (site size, and number recruited prior to SWAT implementation included in their continuous form) will be performed. Feasibility outcomes will be reported descriptively.

The FLARE SWAT protocol will be registered on the Northern Ireland MRC Trials Hub for Methodology Research SWAT registry.

The results will be combined in a meta-analysis with those of SOFFT (ISRCTN 87904264) to increase the power of the analysis.

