The study has a total 22-month recruitment period, including an internal pilot phase of 8 months at the start followed by the main recruitment period. Recruitment will take place at up to 40 participating NHS Trusts. Following randomisation and treatment, all participants will be followed up for six months. This includes three clinic visits (either face-to-face or remotely) for data collection at up to one week, then six weeks and three months (visits should coincide with visits that occur as part of routine care) post-surgery and randomisation. Participants will be asked to self-report outcome data via completion of questionnaires at baseline, six weeks, three months and six months postsurgery by email, telephone or post, as per the study flow chart and schedule of assessments.

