5.6 Project Management and Data Monitoring

5.6.1 Project Management

The project will be sponsored by South Tees Hospitals NHS Foundation Trust.

Each site will have a site PI who will be responsible locally for the study and where possible an Associate PI (API) who will be a trainee surgeon or another appropriate member of the research team. APIs will be encouraged to register with the NIHR API scheme.

YTU is undertaking the duties formally delegated by the trial Sponsor.

The trial manager at YTU will be responsible for all aspects of trial management. They will be supported by a trial co-ordinator(s), who will be responsible for the day-to-day support of trial sites, coordinate recruitment, data handling, and the management of the administrative trial team. The team at YTU will meet on a regular basis during the study and will work closely with the co-chief investigators (CIs), particularly at the start of the project and during the internal pilot of the study, including regular teleconferences to ensure that all aspects of preparation of study material, study site setup and the start of recruitment progress smoothly. They will keep in close contact via email and telephone throughout.

The primary responsibility for monitoring the safety of participants in clinical trials lies with the trial Sponsor. Data monitoring will be undertaken by the Trial Management Group (TMG), TSC, and a Data Monitoring Committee (DMC), on behalf of the Sponsor and Funder. The project will also be monitored by the Sponsor for whom a representative will be invited to attend the TMG and TSC meetings. The minutes/records of these meetings will be stored at YTU and will be shared with the sponsor on a routine basis.

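### The embedded recruitment study (SWAT) randomises trainee APIs but analyses site recruit counts with a plain Poisson model that makes no allowance for between-site variation, so its intervals are likely to be too narrow.

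*Protocol*

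**What the plan says.** Protocol Section 4.11.2 sets up a two-by-two comparison of an enhanced API package and a digital nudge. The unit randomised is the trainee: "Trainee APIs will be randomised to one of four interventions". The outcomes are counted by site: "The primary outcome will be the number of recruits at a site during the six months the API is in post", and "A secondary outcome will be the total number of recruits over the six months following the API being in place". The analysis is "A Poisson regression model, containing the two interventions (enhanced API and digital nudge) and the minimisation factors", and those factors are "site size, and number recruited prior to SWAT implementation included in their continuous form", so both covariates also belong to the site.

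The section gives no site effect, clustered or robust standard error, or overdispersion term. It does not say how many APIs a site may contribute, or how a second or concurrent API would be allocated. It also states no SWAT sample size, power or target effect. The SAP (Section 1) is confined to the clinical effectiveness analysis and does not cover the SWAT. The protocol adds that "The FLARE SWAT protocol will be registered on the Northern Ireland MRC Trials Hub for Methodology Research SWAT registry"; that document was not available for this review.

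**The concern.** A Poisson model takes the variance of a count to equal its mean. That fails when sites with the same covariate values have different underlying recruitment rates, as hand trauma centres with different case-mix, staffing and theatre access plausibly do. The standard errors are then too small, the intervals too narrow, and an ineffective recruitment aid is declared effective more often than 5% of the time. This needs only one API per site. If a site contributes several, its counts are also correlated with each other.

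The protocol intends to pool the result with that of a second host trial. An understated standard error would then give the FLARE estimate too much weight, if inverse-variance weights are used.

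**Working it through.** **Inputs from the documents.** A post lasts six months (Protocol 4.11.2). The target is one recruit per site per month (3.1 and 4.11.1), so the mean count per post is μ = 6. Up to 40 sites, 22 months of recruitment (Section 3) and 310 participants (5.5.2).

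**Assumptions.** 20 sites in the no-covariate simulation; between-site variation of 0.2, 0.4 or 0.6 (coefficient of variation of the site rate, close to the SD on the log scale); no true effect. The SWAT section states no power or sample size, so there is no figure to reproduce.

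**Step 1: size of the problem before covariates.** If site rates vary with coefficient of variation c, then Var(Y) = μ(1 + μc²), whereas Poisson assumes μ. The true standard error is r = √(1 + μc²) times the reported one, and the actual two-sided error at a nominal 5% is 2[1 − Φ(1.96/r)].

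| c | 1 + 6c² | r | 1.96/r | Error by formula | Simulated, one post per site |
|---|---|---|---|---|---|
| 0.2 | 1.24 | 1.11 | 1.76 | 8% | 6% |
| 0.4 | 1.96 | 1.40 | 1.40 | 16% | 15% |
| 0.6 | 3.16 | 1.78 | 1.10 | 27% | 26% |

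Formula and simulation agree closely. With three separately randomised posts per site the simulated errors are about 7%, 14% and 25%. The inflation therefore comes from between-site variation and does not need successive trainees.

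**Step 2: with both planned covariates.** Site size and prior recruits absorb part of the between-site variation. Simulated type I error falls to about 5-9%, 10-12% and 13-19% at SDs of 0.2, 0.4 and 0.6, again even with one post per site. Inverting the formula, r = 1.96/z, where z is the upper p/2 normal point for an error rate p:

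- SD 0.2: 1.96/1.96 = 1.00 to 1.96/1.695 = 1.16
- SD 0.4: 1.96/1.645 = 1.19 to 1.96/1.555 = 1.26
- SD 0.6: 1.96/1.514 = 1.29 to 1.96/1.311 = 1.50

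At an SD of 0.4, honest intervals would be about 19-26% wider on the log scale. Under inverse-variance pooling, the study would otherwise carry r² = 1.42 to 1.59 times its proper weight.

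**Step 3: does the repair work?** Without covariates, site-clustered standard errors bring the error to about 6-7%. With the covariates they give about 5-10%. The remaining excess reflects the small number of sites, hence the small-sample correction below.

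**Step 4: could a site contribute more than one post?** 22/6 = 3.7, so at most three full posts fit, and two at a site open 12 to 14 months. At one recruit per site per month, 310 recruits are 310 site-months: 310/20 = 15.5 months per site with 20 sites (two full posts), or 310/40 = 7.75 with 40 (one). Repeat posts are possible but not stated.

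**Step 5: the secondary window.** Its start is ambiguous. If it runs from the end of a post and another API follows at once, it is the same six months as the successor's primary window, with about 6 shared recruits at the target rate. If it runs from the start of the post, it repeats the primary outcome.

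**The case against.** Section 4.11.2 is a summary, and the separate SWAT protocol may already specify robust errors and a rule for repeat APIs. That stands as a caveat. However, the protocol section does name the model and its terms, and none of them handles between-site variation. The between-site SDs are also assumptions: at 0.2 the covariates leave little or no inflation.

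A reader might infer more: that successive trainees at a site cross between arms, that an earlier trainee's effect carries over and dilutes the comparison, and that recruits are counted under two allocations. The documents do not support this.

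- No section says that a site supplies more than one randomised API or that a later one is randomised afresh. Section 5.6.1 describes "where possible an Associate PI (API) who will be a trainee surgeon or another appropriate member of the research team". The plural in Section 4.11 refers to sites in general, and a single pre-SWAT recruitment count is compatible with one allocation per site.
- Consecutive posts do not overlap, so each recruit enters the primary outcome once. Sharing would need concurrent APIs, or one API's secondary window coinciding with the next API's primary window.
- Carry-over need not bias the estimate. With an assumed true rate ratio of 1.3, additive carry-over leaves it at 1.29-1.31. Only if an already exposed site gains nothing more does it fall, to about 1.23 with half carry-over or 1.15 with full.
- A scenario of 20 sites, three posts and six recruits per post implies 20 × 3 × 6 = 360 recruits, more than the 310 planned.

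Nor do the documents show that sites should be randomised instead of trainees. In that same scenario (SD 0.4, rate ratio 1.30, clustered analysis), simulated power is about 22% with one allocation per site. With posts randomised it is 56%, 37% and 17% under no, half and full carry-over. Randomising trainees is a defensible trade-off.

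**Conclusion.** The concern holds for the inference. The stated Poisson model understates uncertainty wherever sites vary beyond the two covariates, even with one API per site. At an assumed between-site SD of 0.4 the type I error is about 10-12% rather than 5%; the range is about 5-9% at 0.2 and 13-19% at 0.6. These figures rest on the assumed SDs and the target recruitment rate, and on the unseen SWAT protocol not already dealing with the matter.

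The handling of repeat or concurrent APIs and the start of the secondary window are gaps to close, not demonstrated errors. The point concerns the embedded methodology study only. It affects neither patients nor FLARE's primary analysis.

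**What to change.** In Section 4.11.2 and the SWAT protocol:

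1. Keep the Poisson mean model with the two interventions and two covariates, and base inference on site-clustered robust standard errors with a small-sample correction. A site random effect or an overdispersion term is an acceptable alternative.
2. State whether a site may contribute more than one randomised API, in succession or together, and how each is allocated. If any site does, add an analysis restricted to the first API post per site.
3. State when the secondary window starts and ends. Where it coincides with a successor's primary window, say so and do not treat the two results as independent.

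If the SWAT protocol already covers these points, a cross-reference is enough. The cost is a few sentences and wider intervals (about 19-26% at an SD of 0.4), which reflect the uncertainty actually present. Changing the unit of randomisation to the site is not required.
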